10 RISK / BENEFIT ASSESSMENT

- **10.1** Anticipated risks. Describe the reasonably foreseeable risks of harm, discomforts, and hazards to the subjects and others of the research procedures. For each harm, discomfort, or hazard:
 - Describe the magnitude, probability, duration, and/or reversibility of the harm, discomfort, or hazard, AND
 - Describe how you will manage or reduce the risks. Do not describe data security protections here, these are already described in Question 9.6.
 - Consider possible physical, psychological, social, legal, and economic harms, including possible negative effects on financial standing, employability, insurability, educational advancement or reputation. For example, a breach of confidentiality might have these effects.
 - Examples of "others": embryo, fetus, or nursing child; family members; a specific group.
 - Do not include the risks of non-research procedures that are already being performed.
 - If the study design specifies that subjects will be assigned to a specific condition or intervention, then the condition or intervention is a research procedure even if it is a standard of care.
 - Examples of mitigation strategies: inclusion/exclusion criteria; applying appropriate data security measures to prevent unauthorized access to individually identifiable data; coding data; taking blood samples to monitor something that indicates drug toxicity.
 - As with all questions on this application, you may refer to uploaded documents.

Because the TcPO2 (tissue oxygen) electrode is heated to 44°C (111°F), there is a minor risk for a thermal injury (skin redness or a minor skin burn) under a less than quarter size area. In our previous study, where the subjects were supine for 55 minutes with the electrode heated to 44°C (40-minutes loaded conditions/15 minutes unloaded condition), we had no alterations in skin integrity or subject reports of adverse events. In this current study, the electrode will be in contact with the subject at the maximum temperature for 135 minutes (120 minutes loaded condition and 15 minutes unloaded).

The TcPO2 electrode is used in clinical practice in both healthy and critically ill neonates and adults. Relevant to this proposal are studies that use TcPO2 under loaded conditions. In studies where the electrode is exposed to a pressure load, there have been no reports of thermal injuries. For example, in a study by Wong, nine patients in a long term care facility (age 85 ± 11 years) had TcPO2 electrodes placed on their sacrum (distal to the coccyx but proximal to the anus), trochanters (hip -2 inches medial to the great trochanters) and on the plantar surface of the heels (note – the electrode will be on the sacrum for this proposed study). The subjects were 1) placed lateral for 30 minutes and 2) turned to supine position with the head of bed at 30° for 2 hours with both the sacrum and heels on the bed surface (low-air-loss), and 3) positioned lateral for 2 hours (unloading). Total data collection was approximately 5 hours. Although five subjects had a low TcPO2 (< 40 mm Hg), which indicates impaired perfusion, there were no reports of alteration in skin integrity associated with the electrodes. Two actions that have been successfully used in other protocols (including our previous study) will be taken to minimize the risk. The sacral electrode will be surrounded by a callus pad to offload any pressure directly on the electrode. If the TcPO2 on the weighted electrode decreases to 0 mm Hg, the temperature on the electrode will be decreased to 37°C for the remainder of the loaded period. At the completion of the study and removal of the TcPO2 sensor, the skin will be inspected. If there is redness that persists, the subject will be instructed to apply topical (such as aloe vera) if so desired. It they are concerned regarding skin condition, the study monitor (a nurse practitioner) will be asked to evaluate the subject and as appropriate refer for any treatment.

Another strategy to decrease the risk will be repeated assessment of the subject's perceptions of perceived pressure or discomfort using the Category Partitioning Scale (CP-50),

which is a verbal scale that describes discomfort/pressure under each condition. Use of this scale may be more appropriate than a "pain scale" as a subject may or may not experience pain, but rather sense pressure or discomfort. Using the CP-50, the subject is first asked to describe using verbal terms the pressure intensity or discomfort associated with the stimulus (i.e., sacral/buttocks pressure or discomfort). The subject can then fine-tune their assessment using the numeric scores. The final score is the analog number. For purposes of this research, at baseline and every 30 minutes, we will ask the subject to limit their evaluation to the pressure/discomfort sensed on the sacrum/buttocks, but we will also ask the subjects to identify on their body where they are experiencing the most pressure/discomfort.

To protect the subject from undo perceived pressure or discomfort, a threshold of CP-50 score of 40 will be established as the maximum score. If the subject reports a CP-50 score greater than 40, the experiment will be stopped. The subjects will not be informed of this cutoff. (This threshold is consistent with Games study, where a threshold of 45 was used in a study of discomfort associated with prolonged sitting in an unpadded seat.

The CP-50 was used in two studies of Black Hawk UH-60 crewmembers exposed to four hours of sitting in a simulated cockpit on an unpadded seat. 9,10 The CP-50 score increased significantly at each time point (every 30 minutes), and at 240 minutes the score had increased an average of 30 points. In the second study, 10 healthy subjects were exposed to 36 kPA (270 mm Hg) and 44 kPA (330 mm Hg) on the ischial tuberosity and poster thigh for 10 minutes. Application of pressure was associated with increased discomfort on the posterior thigh (5.5 points at 36 kPA and 7.5 points at 44 kPA) and ischial tuberosity (3.1 points/4.2 points, respectively), with increased discomfort at higher pressures. Of importance, in this proposed study the skin interface pressure will be much lower, thus we anticipate lower levels of perceived pressure and discomfort. Based on our previous work, the average sacral/buttocks pressure on the litter plus mattress was 42 ± 12 mm Hg and 60-70 mm Hg on the vacuum spine board. 11

Figure 3. Category Partitioning Scale (CP-50).⁷

Because the area of the body we are interested in is the lower back/buttocks, we will provide pillows for the head and to elevate the heels.

Placement of the Mepilex and performance of the monitoring will require the subject to expose the lower half of their back and upper aspect of their buttocks. The procedures will be conducted with the subject lying facedown. The subject will be appropriately draped to minimize exposure. All procedures will be performed in a screened area and the subject will be asked if they would like a chaperone present during these procedures.

Version 1.8

\	e risks . Are there any risks of the study procedures to men and women (who are subjects, or partner related to pregnancy, fertility, lactation or effects on a fetus or neonate?
	ect teratogenic effects; possible germline effects; effects on fertility; effects on a woman's ability to continue a fects on future pregnancies.
x No	→ If no go to question 10.3
Yes	→ If yes, answer the following questions:
	a. Risks. Describe the magnitude, probability, duration and/or reversibility of the risks.
	b. Steps to minimize risk . Describe the specific steps you will take to minimize the magnitude, probability, or duration of these risks.
	Examples: inform the subjects about the risks and how to minimize them; require a pregnancy test before and during the study; require subjects to use contraception; advise subjects about banking of sperm and ova.
	If you will require the use of contraception: describe the allowable methods and the time period when contraception must be used.
	c. Pregnancy. Describe what you will do if a subject (or a subject's partner) becomes pregnant
	For example; will you require the subject to immediately notify you, so that you can discontinue or modify the study procedures, discuss the risks, and/or provide referrals or counseling?
adverse reac who received severe allerg a. Describe h	nagement. Answer this question only if your subjects will receive MRI scans. A rare but serious tion called nephrogenic systemic fibrosis (NSF) has been observed in individuals with kidney disease digadolinium-based contrast agents (GBCAs) for the scans. Also, a few healthy individuals have a ic reaction to GBCAs. ow you will assess the renal function of your subjects prior to MRI scans and how you will use that on to exclude subjects at risk for NSF.
Not appl	icable
•	our protocol for handling a sever allergic reaction to the GBCA or any other medical mergency during the MRI scan, including who will be responsible for which actions.
Not appli	icable
10.4 Unforeseeak	ole risks. Are there any research procedures that may have risks that are currently unforeseeable?
Example: usin	g a drug that hasn't been used before in this subject population.
x No	
Yes	→ If yes, identify the procedures.

•	o will be under regional or general anesthesiology. Will any research procedures occur while
•	ents are under general or regional anesthesia, or during the 3 hours preceding general or regional
	supplied for non-research reasons)?
X No	
Yes	→ If yes, check all the boxes that apply.
	Administration of any drug for research purposes
	Inserting an intra-venous (central or peripheral) or intra-arterial line for research purposes
	Obtaining samples of blood, urine, bone marrow or cerebrospinal fluid for research purposes
	Obtaining a research sample from tissue or organs that would not otherwise be removed during surgery
	Administration of a radio-isotope for research purposes**
	Implantation of an experimental device
	Other manipulations or procedures performed solely for research purposes (e.g., experimental liver dialysis, experimental brain stimulation)
	If you checked any of the boxes: You must provide the name and institutional affiliation of a physician anesthesiologist who is a member of your research team or who will serve as a safety consultant about the interactions between your research procedures and the general or regional anesthesia of the subject-patients. If your procedures will be performed at a UW Medicine facility or affiliate, the anesthesiologist must be a UW faculty member, and you must consult with the Vice Chair of Clinical Research in the UW Department of Anesthesiology and Pain Medicine for feasibility, safety and billing.
	** If you checked the box about radio-isotopes: you are responsible for informing in advance all appropriate clinical personnel (e.g., nurses, technicians, anesthesiologists, surgeons) about the

10.6 Data and Safety Monitoring. A Data and Safety Monitoring Plan (DSMP) is required for clinical trials (as defined by NIH). If required for your research, upload your DSMP to the **Supporting Documents** SmartForm in **Zipline**. If it is embedded in another document you are uploading (for example, a Study Protocol, use the text box below to name the document that has the DSMP.

In our previous research, which used similar methods, the IRB determined that the study was minimal risk and a medical monitor/DSMB was not required. DSMP v1 ([name]) is attached.

10.7 Un-blinding. If this is a double-blinded or single-blinded study in which the participant and/or you do not know the group to which the participant is assigned: describe the circumstances under which un-blinding would be necessary, and to whom the un-blinded information would be provided.

Not		

appropriate clinical personnel (e.g., nurses, technicians, anesthesiologists, surgeons) about the administration and use of the radio-isotope, to ensure that any personal safety issues (e.g., pregnancy) can be appropriately addressed. This is a condition of IRB approval.

10.8 Withdrawal of participants. If applicable, describe the anticipated circumstances under which participants will be withdrawn from the research without their consent. Also, describe any procedures for orderly withdrawal of a participant, regardless of the reason, including whether it will involve partial withdrawal from procedures and any intervention but continued data collection or long-term follow-up.

The subject will be withdrawn in they report discomfort about the specified threshold. Although we do not anticipate a subject having intolerance to lying in the stiff vacuum spine board, if they indicate intolerance to the compression (e.g., a sense of claustrophobia), we will offer them the opportunity to discontinue their participation. We will obtain post-measures (skin cytokines and moisture) and record final tissue oxygen and skin temperature measurements at the time of withdrawal. All study data will be retained.

10.9 Anticipated direct benefits to participants. If there are any direct research-related benefits that some or all individual participants are likely to experience from taking part in the research, describe them below:

Do not include benefits to society or others, and do not include subject payment (if any). Examples: medical benefits such as laboratory tests (if subjects receive the results); psychological resources made available to participants; training or education that is provided.

There is no direct benefit to participants.

- 10.10 Individual subjects findings.
 - a. Do you anticipate that the research will produce any urgent, clinically actionable results?

These may be results from screening procedures, results that are actively sought for purposes of the study or they may be results that are discovered unintentionally. Examples include high calcium levels, liver function test results, and a mass on an MRI that may indicate a tumor, a diagnostic discrepancy, and suicidal intentions.

- → If yes, the results should be shared with the subject(s). Complete and upload the SUPPLEMENT: Participant Results Sharing to the Supporting Documents SmartForm of Zipline
- **b**. Do you plan to share any other results of your study procedures or findings with the subjects such as genetic test results, laboratory tests, etc.?

You should answer YES if your consent form says anything about sharing individual information with subjects.

→ If yes, complete and upload the SUPPLEMENT: Participant Results Sharing to the Supporting Documents SmartForm of *Zipline*

10.11 Commercial products or patents. Is it possible that a commercial product or patent could result from this study?

х	No
	Yes

→ If yes, describe whether subjects might receive any remuneration/compensation and, if yes, how the amount will be determined.

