Placement of Sensors: After completion of the height, weight and body fat measurements, the subject will lie down on the study surface and the temperature/oxygen sensors will be placed on the lower aspect of their back and one oxygen sensor placed on their chest (approximately 2 inches below the collar bone on the left chest). The transcutaneous oxygen (TcPO2) probes will heat up to 111°F, as recommended by the device manufacturer.

The subject will rest on their side for approximately 15 minutes while the measurements from the sensors to stabilize. These sensors allow for continuous measurement of skin tissue oxygenation and temperature.

Stabilization: Following acclimation, the subject will be assisted to a side lying position (unloaded) and the temperature and TcPO2 probes will be placed. Based on our previous research, it takes approximately 15 minutes for the sacral probe to stabilize ($TcPO_2 < \pm 2 \text{ mm Hg for 4 minutes}$).

Cytokine/Skin Moisture Measurements: After stabilization four small pieces of tape (Sebutape) will be placed on the lower back for 1 minute for the measurement of interleukin 1/Total protein. The Sebutape (size: 0.75 x 1.1 inches) will be placed in four quadrants (sacrum/buttocks). Sebutape has been used to measure IL- α in studies related to pressure and shear; including the evaluation of Mepilex under conditions of pressure and shear. Removal of the tape causes minimal stripping of the stratum corneum and discomfort to the subject. The Sebutape will be handled using blunt tweezers and gloved hands to avoid any cross contamination. Four patches will be applied (two on sacrum/two on buttocks) to intact, unblemished skin that is free of excessive hair, but which allows us to characterize potential injury on the buttocks and sacrum (areas of pressure injuries noted in Mok's study). After the one-minute sampling period the Sebutape will be removed using blunt tweezers and will be placed flat (avoid any crumpling or folding) into an individually labeled vial and immediately frozen on ice.

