Skin Moisture. We will also use a noninvasive probe to measure the amount of moisture in the skin on the lower back/sacrum. Two components of skin moisture will be measured: 1) Epidermal moisture, which reflects perspiration and 2) subepidermal moisture using a Delfin MoistureMeter D (Delfin Technologies, LTD, Grennwich, CT) dermal phase meter (http://www.delfintech.com/en/product_information/moisturemeterd/). Epidermal moisture (stratum corneum) will be measured at 0.5 mm below the skin surface and subepidermal moisture (i.e., below the epidermal stratum corneum layer) will be measured at a depth of 2.5 mm. The device consists of a control unit (signal producer) and a probe (open-ended coaxial transmission line), which is placed in contact with the skin The skin moisture will be measured at a standardized site, mid-sacrum, approximately 2 cm above the gluteal fold (avoiding the sites of the Sebutape). This location will be marked with ink pen to assure the same location for repeat measurement. For each depth, the probe will be placed on the skin surface and held for 5 seconds.

After these measurements are complete, subjects in the Mepilex dressing groups will have the dressing placed on their lower back/buttocks. All subjects will then complete an additional 5 minutes in the side-lying position, after which they will lie on their back on the designated surface. After positioning a sheet will be placed over the subject for comfort. A pillow may be placed under the head and heels at the subject's discretion.

The skin interface pressure will be measured continuously during the loaded period using the XSensor™ System (Crown Therapeutics, Belleville IL) with X3 Medical v6.0 software. This pad, which is similar to a sheet, will be positioned on the surface. *Peak skin-interface pressure*, which is the highest measured pressure for each body region and the *Peak Pressure Index* (PPI), which is the average of a 3 x 3 sensor area representing the highest pressure (including the peak pressure cell). The sacrum/buttocks will be divided into four quadrants based on the vertebral column and top of the gluteal cleft.⁵⁵ For the Mepilex groups, the pressure on the surface of the Mepilex will be recorded. Although this procedure does not directly measure skin interface pressure, which may be decreased by the Mepilex, it is not possible to place the pressure mat between the Mepilex and the skin.

Unique Procedures by Study Group

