For all groups the stretcher is placed on the bedframe of a standard hospital bed. The stretcher is secured to the bed frame. This elevation on the bedframe is for ease of access for the subjects. The bedframe is in the low position, such that the subjects will be approximately 2-3 feet off the floor.

Aeromedical Evacuation (AE) conditions

Group 1: Mepilex: Litter + AE mattress + 30° backrest elevation. Subjects will be positioned supine on the litter plus AE mattress. Mepilex will be placed on sacrum/buttocks region. Subjects will be asked to lie supine with

limited motion for 120 minutes. After completion of the 120-minute supine period, subject will be positioned side-lying. After 5 minutes side-lying, the Mepilex will be removed and the skin moisture and skin cytokine measurements will be obtained. After completion of the 15-minute side-lying phase, the skin sensors will be removed, and the study will be complete

Group 2: Without Mepilex: Litter + AE mattress + 30° backrest. Subjects will be positioned supine on the litter plus AE mattress. Subjects will be asked to lie supine with limited motion for 120 minutes. No Mepilex will be used. After completion of the 120-minute supine period, subject will be positioned side-lying. After 5 minutes side-lying the skin moisture and skin cytokine measurements will be obtained. After completion of the 15-minute side-lying phase, the skin sensors will be removed, and the study will be complete

AE Conditions with Vacuum Spine Board

Subjects in Groups 3 and 4 will be positioned on the vacuum spine board (VSB), which will be place on top of the litter + AE mattress. The litter will be elevated to 30 degrees (consistent with current practice). The vacuum will be applied according to manufacturer's recommendations. After creation of the vacuum, the VSB will be loosened around the head and feet to allow for movement for comfort. These steps do not interfere with the thoracolumbar stabilization or the interface pressure over the sacrum/buttocks. To simulate en-route care the vacuum will be maintained for 30 minutes (simulate movement to the aircraft). At 30 minutes, the

vacuum will be released with the straps in place (simulate current en route practice). At 90 minutes, the vacuum will be reapplied for 30 minutes to simulate descent and landing phase of flight (total time 120 minutes).

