The VSB straps will be in place but loosened (the photo shows the straps tightened – as they would be during transport). The subject's arms will be free (the additional litter straps – seen as olive green in the photo across the upper legs and chest will not be used). The straps will remain clipped to enhance stability of the VSB, but the subject will be able to move their arms and legs and release the straps if so desired.

Group 3: Mepilex: Vacuum Spine Board (VSB) placed on litter + AE mattress. Subject will complete above procedure. Mepilex will be placed on sacrum/buttocks before positioning on VSB. After completion of the 120-minute supine period, the vacuum will be released, and the subject will be positioned side-lying. After 5 minutes side-lying, the Mepilex will be removed and the skin moisture and skin cytokine measurements will be obtained. After completion of the 15-minute side-lying phase, the skin sensors will be removed, and the study will be complete.

Group 4: Without Mepilex: Vacuum Spine Board (VSB) placed on litter + AE mattress: Subject will complete above procedure. No Mepilex. After completion of the 120-minute supine period, the vacuum will be released, and the subject will be positioned side-lying. After 5 minutes side-lying, the skin moisture and skin cytokine measurements will be obtained. After completion of the 15-minute side-lying phase, the skin sensors will be removed, and the study will be complete

Prolonged Field Care (PFC) conditions

Subjects in the prolonged field care groups (Groups 5 and 6) will lie on the Talon litter supine (no mattress/no head of bed elevation). Pillows may be placed under the head/heels for comfort. Subjects will be asked to remain as still as possible during the 120-minute supine period. Upon completion of the supine period, subjects will be positioned side-lying for 15 minutes. Skin moisture and skin cytokine measurements will be obtained 5 minutes after the subject is positioned side-lying. After completion of the 15-minute side-lying phase, the skin sensors will be removed, and the study will be complete

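### Does the 135-minute electrode contact time in Protocol section 10.1, which omits the heated period before loading, call for a change to the plan?

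*Protocol*

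**What the plan says.** Section 10.1 of the Protocol names thermal injury under the heated electrode as a risk and states the exposure: "the electrode will be in contact with the subject at the maximum temperature for 135 minutes (120 minutes loaded condition and 15 minutes unloaded". It sets this beside the investigator's earlier study, given as 55 minutes (40 loaded plus 15 unloaded).

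Section 5.1 gives the sequence from which exposure can be counted:

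- After the 20-minute acclimation, "the subject will be assisted to a side lying position (unloaded) and the temperature and TcPO2 probes will be placed". The sensor-placement paragraph adds: "The transcutaneous oxygen (TcPO2) probes will heat up to 111°F".
- On the wait for a stable reading: "Based on our previous research, it takes approximately 15 minutes for the sacral probe to stabilize".
- Baseline sampling follows: "After stabilization four small pieces of tape (Sebutape) will be placed on the lower back for 1 minute".
- After the moisture readings, and the dressing where assigned: "All subjects will then complete an additional 5 minutes in the side-lying position".
- The 120-minute supine period comes next. For the Talon litter groups, "Upon completion of the supine period, subjects will be positioned side-lying for 15 minutes"; the other groups have a phase of the same length.
- Removal in every group: "After completion of the 15-minute side-lying phase, the skin sensors will be removed".

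**The concern.** Section 5.1 has the heated probe on the skin in two unloaded periods, one before loading and one after. Section 10.1 counts only one of 15 minutes. Whichever period its author had in mind, the other is missing, so the stated time at full temperature looks too short.

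The figure describes how long a healthy volunteer is exposed to a named hazard, in a section whose prompt lists duration among the features of a risk to be described, and it applies to all six groups. The longer exposure is also the stated difference from the earlier study that is cited in support of safety. If 135 were materially low, the ethics committee would have judged the risk on the wrong exposure. If a safeguard were tied to elapsed time, it could be set wrongly.

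**Working it through.** **The plan's own figure.** 120 + 15 = 135 minutes. It reproduces, so the only question is which phases it covers.

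**Inputs from section 5.1, in minutes**

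| Phase with probe on | Time |
|---|---|
| Stabilisation, side-lying | about 15 |
| Tape sampling | 1 |
| Further side-lying before loading | 5 |
| Supine, loaded | 120 |
| Side-lying after loading | 15 |

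Acclimation is left out because the probes go on after it. The 15-minute wait is described twice in section 5.1 and is counted once. The post-loading measurements at 5 minutes fall inside the final 15 minutes and add nothing. The two 5-second moisture readings (10 seconds in all) are ignored.

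**Sums**

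- Timed blocks after stabilisation, without tape: 5 + 120 + 15 = 140.
- With tape: 1 + 5 + 120 + 15 = 141. This does not depend on how long stabilisation takes.
- Placement to removal: 15 + 1 + 5 + 120 + 15 = 156, plus untimed handling.

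**Gap from 135**

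- If all of stabilisation is warm-up: 141 − 135 = 6; 6/135 = 4.4%.
- If none of it is: 156 − 135 = 21; 21/135 = 15.6%.

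**How firm the range is.** The upper figure assumes instant warm-up, yet it excludes handling time, so it is neither reachable exactly nor a ceiling. The stability criterion needs 4 minutes of steady readings. If a steady reading requires full temperature (an assumption), the lower figure becomes 141 + 4 = 145. If the four tapes are applied one after another (an assumption, 4 minutes in place of 1), the range becomes 144 to 159. The supportable statement is at least about 140 minutes, with the exact time not determinable.

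**Could 135 still be right?** Warm-up would have to last 156 − 135 = 21 minutes, longer than stabilisation itself. The step-down to 37°C does not explain it either. It applies only if the reading on the weighted electrode falls to zero, and section 10.1 counts all 120 loaded minutes at full temperature, so 135 already assumes no step-down.

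**Effect on the comparison with the earlier study.** Let x be the heated time before loading, taken as equal in both studies.

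- Added exposure: (135 + x) − (55 + x) = 80 minutes for any x.
- Ratio as stated: 135/55 = 2.45. With x = 6: 141/61 = 2.31. With x = 21: 156/76 = 2.05.

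On that assumption the stated figures do not understate the increase. In the opposite extreme, where the earlier study had no heated time before loading, the increase would be 141 − 55 = 86 to 156 − 55 = 101 minutes. The documents do not give that study's schedule. Section 5.1 does draw its 15-minute stabilisation time from previous research, and section 1.8b says the same measures are carried over. A shared way of counting is therefore the likelier reading.

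**What depends on 135.** The safeguards in section 10.1 are a pad around the sacral electrode, a step-down triggered by the oxygen reading, skin inspection at removal, and discomfort scores at baseline and every 30 minutes. None is triggered by total heated time. The SAP does not use the figure.

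**The case for a change.** The strongest case for an edit is that section 10.1 describes a physical quantity, contact at full temperature, and states no counting convention. No reading of section 5.1 for a completed session without step-down yields 135; even the barest count gives 140. The sentence gives the exposure time for a hazard to volunteers, and correcting it would cost one line.

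The disagreement itself stands. Heating might be delayed until loading, but section 5.1 puts heating in the sensor-placement step and needs a stable reading before baseline sampling. If heating is in fact delayed, section 5.1 is the part that misdescribes the session.

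The consequence does not stand. Section 10.1 labels the two components of its total, and section 5.1 of the same form sets out every phase, so the committee had the full sequence before it. Section 10.1 also cites a loaded-electrode study with about 5 hours of data collection and no reported alteration in skin integrity. Its electrode temperature is not given, so this is only partial reassurance. The earlier study's record of no zero-flow cases came from 40 minutes of loading and says little about 120; nothing here rests on it. Restating the earlier 55 minutes on a fuller basis would need facts that the documents do not contain.

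**Conclusion.** The inconsistency is real, small and without consequence for the trial. Section 10.1 leaves out the heated period before loading. It is low by 5 or 6 minutes at the least and by about 21 at the nominal top. This rests on a completed session, no step-down, tapes applied together and stabilisation of about 15 minutes.

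No change to the plan follows. What a subject undergoes is governed by section 5.1, which is complete, and the safeguards respond to readings, skin condition and reported discomfort, not to the total. The comparison with the earlier study probably holds, on the assumption that both studies count time in the same way. As wording, the two sections do need reconciling, which can be done whenever the form is next revised. I take no view on which section is right, or on electrode temperature or exposure time. I am confident of the mismatch, but not of any single figure for time at full temperature.
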